#### **Statistical issues:**

### Primary outcomes:

The research question is whether statins can benefit breast cancer patients with dyslipidemia (low and medium risk of ASCVD). The main endpoint was DFS. A review of the literature suggests that simvastatin reduced the recurrence rate of breast cancer by 10%. The investigator would like to be able to detect a difference of 10% or more in DFS change between the two groups. How many patients are required in each group at  $\alpha$  (two-sided) = 0.05;  $\beta$  = 0.10, power = 0.90.

1. Null Hypothesis: For breast cancer patients with dyslipidemia (low and medium risk of ASCVD) under endocrine therapy, whether statin used is the same in DFS.
2. Alternative Hypothesis (two-sided): For breast cancer patients with dyslipidemia (low and medium risk of ASCVD) under endocrine therapy, whether statin used is different in DFS.
3. Effect size=0.1(10%\*2)
4. Standard deviation of CTC=1
5. Standardized effect size=effect size/standard deviation=0.1/1=0.1
6.  $\alpha$  (two-sided) = 0.05;  $\beta$  = 0.10, power = 0.9
7. Based on Appendix 6A from the text book, the estimated sample size is 157 in each group.
8. Ultimate sample size =  $2*157/0.9= 348$

Looking across from a standardized effect size of 0.10 in the leftmost column in Table 6A and down from  $\alpha$  (two-side) =0.05 and  $\beta$  = 0.10 is the required sample size of 157patients in statins group and control group. With 10% dropout the final sample size is 348[14].

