### **Data safety & monitoring:**

The members of DSMB are 3 professors in the breast surgery department, 6 attending doctors and 3 residents. DSMB members will meet:

- 1) before the start of the trial to discuss the study protocol,
- 2) at early stage of about 10-20 patients are enrolled. In order to monitor **enrollment** efficacy, **adverse effects** that might have happened, the efficacy of **blinding** strategy, the current **outcome variables** in control and interventional group (only known to DSMB members), **protocol** compliance and quality control issues.
- 3) Subsequent DSMB meetings will be hold regularly (at least every three months) or anytime when there are safety issues, need to stop the program earlier and so on.

If DSMB find that the statins are causing harm, they could discuss whether to end the study early after balancing between ethical responsibility to the participants and the advance of scientific knowledge.

If DSMB find that the statins are much more effective than anticipated, they could stop the study before the primary endpoint.

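### The DSMB may stop for benefit on an unquantified criterion, with no boundary, event minimum or adjusted level, so the two-sided 0.05 is not guaranteed

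*Combined protocol and SAP*

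**What the plan says.** The benefit provision is in Data safety & monitoring: "If DSMB find that the statins are much more effective than anticipated, they could stop the study before the primary endpoint". The same section describes an early meeting at about 10–20 enrolled patients, where the board sees outcome variables "in control and interventional group (only known to DSMB members". Later meetings are regular, "at least every three months) or anytime when there are safety issues, need to stop the program earlier and so on". No maximum number of meetings is given. The content of the later meetings is not listed; by-arm review there is implied by the power to stop for benefit, not stated. A separate provision covers harm: "If DSMB find that the statins are causing harm, they could discuss whether to end the study early".

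The only error level in the document is under Primary outcomes, "two-sided) = 0.05", with no allowance for interim looks. That section is also the only place that could define what was anticipated, and it does so in two ways: "A review of the literature suggests that simvastatin reduced the recurrence rate of breast cancer by 10" per cent, and "The investigator would like to be able to detect a difference of 10% or more in DFS change between the two groups". It gives no control-group DFS rate. The Abstract names a log-rank test and says that the board will review the study periodically. It gives no interim rule.

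**The concern.** A two-sided 0.05 describes one test done once. When a board can look repeatedly at a comparison and end the trial on a favourable result, chance highs along the way become extra opportunities for a false positive, unless the interim criterion is strict or the level is adjusted. Here the criterion is a phrase whose reference value is itself unclear, so neither the board nor a reader can work out the error actually run. Estimates at an early benefit stop are also too favourable on average, and with few DFS events they are unstable. A positive early stop could then not be defended at the stated 5%.

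**Working it through.** **Inputs from the document.** Two-sided 0.05 and "the estimated sample size is 157 in each group" (Primary outcomes), so 2 × 157 = 314 patients; a window of 5 calendar years (Abstract); meetings at least every three months (Data safety & monitoring).

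**Assumed, because the document is silent.** Control 5-year DFS 70–90%, exponential DFS, uniform accrual over 1–4 years, quarterly efficacy looks once 10 events are expected (5–16 interim looks), interim stops for benefit only, final two-sided log-rank test at 0.05.

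**1. The plan's own figures.** With no interim stop, the simulated error is 0.0498, as stated. The 157 does not follow from its inputs: 2 × (1.960 + 1.282)² / 0.1² ≈ 2,102 per group. That is a separate matter; 157 is used here only to set the number of patients.

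**2. What was anticipated.** HR = ln(S statin) / ln(S control).
- Absolute 10 points, 80 to 90%: ln 0.9 / ln 0.8 = 0.47.
- Absolute 10 points, 70 to 80%: ln 0.8 / ln 0.7 = 0.63.
- Relative 10% fall in recurrence, for example 20% to 18%: ln 0.82 / ln 0.80 = 0.89 (0.88–0.90 over the assumed range).

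A requirement of k times the anticipated log HR means an observed HR below HR^k.

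**3. Error under the null.** At a look with d events, the information is I = d/4, the score W has variance I, Z = W/√I, and the estimated log HR (in the direction of benefit) is W/I. A trial counts as positive if an interim look meets the criterion in favour of statins, or if the final |Z| > 1.96.

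| Interim criterion | False-positive chance |
|---|---|
| p<0.05 | about 8–13% |
| p<0.05 and 1.5 times, 80 to 90% / 70 to 80% | 7.7–8.0% / 10.5–11.0% |
| p<0.05 and 2 times | about 5.5% / about 9% |
| p<0.05 and 2.5 times | 5.0–5.1% / 7.0–7.8% |
| p<0.05 and 3 times | 5.0% / 5.5–6.0% |
| p<0.005 | 5.1–5.7% |
| p<0.001 | 5.0–5.2% |

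If the 10% is relative, the multiplier adds nothing. At 2.5 times, the threshold is an HR of 0.73–0.76, while p<0.05 at the last interim look already needs 0.39–0.65. The first row then applies. A patient-level log-rank simulation gave 8.8–11.9% for that row. Under the same row, the average HR at an early stop is about 0.29–0.34 when the truth is 0.47, and 0.36–0.42 when it is 0.63.

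**4. Sensitivity.** The 10-event start is an assumption. For nominal p<0.05, starting at 5 events gives about 11–14%. Starting at 20 gives about 5.6–11% where any interim look remains.

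**5. One look at half the events, p<0.001 for benefit, final 0.05.** The two statistics have correlation √0.5. P(Z₁ > 3.29) + P(|Z₂| > 1.96) − P(both) = 0.0501.

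The chance of stopping there under a true 10-point effect is 1 − Φ(3.29 − |ln HR| × √(d/8)), where d is the planned total of events. If follow-up ends with the 5-year window, d is about 72–49 (70 to 80%), 57–39 (75 to 85%) or 43–29 (80 to 90%) for 1–4 years' accrual. With HR 0.472 and d = 42.8: 0.750 × 2.313 = 1.736, and 1 − Φ(1.554) = 0.060. With HR 0.626 and d = 49.3: 0.469 × 2.482 = 1.164, and 1 − Φ(2.126) = 0.017. Patient-level simulation gave 0.010–0.037.

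**The case against.** The strongest reply is that the wording is meant to be strict and the power discretionary. A board that stops only for an effect far beyond expectation may need a result that chance rarely produces, and a board that gives recommendations does not declare success. Much of this stands. At 2.5–3 times an 80-to-90% effect, the error is 5.0–5.1%. Inflation also needs the further premise that a benefit stop is reported as a positive finding. But discretion exercised after seeing results by arm does not control error, and the strict reading is only one that the text permits.

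A reader might infer that most readings of the provision exceed 5%. The document does not support that: it gives no set of readings to count, and several natural ones sit at or near 5%. A reader might also take the larger figures from testing at nominal 0.05 at 20 equally spaced looks, about 25% two-sided or 15% with benefit-only stops. Those assume that information accrues evenly from the start and that the board tests at every quarterly meeting; the plan says neither.

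It is also fair to say that the event total is unsettled. The Abstract gives a 5-year calendar window, while the Appendix has a 5-year visit for each patient. With full follow-up, the expected totals are 157 × (0.30 + 0.20) ≈ 79, 157 × (0.25 + 0.15) ≈ 63 or 157 × (0.20 + 0.10) ≈ 47. This affects the timing of any look, not the missing rule.

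**Conclusion.** The concern holds in this form: the plan permits benefit stopping without a criterion that protects its two-sided 0.05, and the reference effect is ambiguous as well. It does not show that the error is necessarily inflated. Under the stated assumptions, the false-positive chance is about 8–13% on nominal p<0.05, about 5.5–11% with 1.5–2 times an absolute 10-point effect, about 5–8% with 2.5–3 times, and near 5% with p<0.001. The omission is certain. Its size rests on assumed DFS rates, accrual, look schedule and first-look event count, and on a benefit stop being reported as positive. The provision should be corrected; the change is small.

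**What to change.** In Data safety & monitoring, replace the benefit sentence with:

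> Stopping for benefit is considered only at one planned comparative DFS look, at half the planned DFS events, and only if the log-rank test favours statins at two-sided p<0.001. The final log-rank test is at two-sided 0.05. No other meeting may stop the study for benefit.

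In item 3, limit the wording on stopping early to safety. Leave the harm provision unchanged. The overall error is then about 0.050.

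The alternative is to state that the board will not stop for benefit, with the same limit on item 3. Deleting the benefit sentence alone is not enough, because item 3 would still allow meetings about stopping early for unspecified reasons. Other prespecified designs, such as alpha spending, would also control the error.

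Under Primary outcomes, state the planned number of DFS events, after reconciling the Abstract's calendar window with the Appendix's per-patient 5-year visit and fixing a control rate. The Abstract also mentions a t-test between groups, so the log-rank test should be named as the primary DFS test.

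The cost is less freedom to stop early. Under a true 10-point effect and the calendar-window event counts, the single look stops the trial only about 1–6% of the time. The look needs no extra patients, because the final test stays at 0.05. Whether 348 patients are enough is a separate question.

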## **Ethical considerations:**

In our study, the major ethical issue is the applied population of statins. In order to mitigate this situation, we will:

- 1) Specify the inclusion criteria that specific patients.
- 2) We will monitor patients' liver function and blood lipid levels and adjust the dosage of drugs accordingly.
- 3) Inform the patients with this potential risk comprehensively, have them better understood the potential risk of this study, and write it in the informed consent.
- 4) Use DSMB to monitor any risk related to the intervention.

Appendix

Statins VS. Dietary Intervention on Breast Cancer Patients

Date: --/-- [dd / mm / yyyy]

Name: \_\_\_\_\_

Address: \_\_\_\_\_

ID No.: \_\_\_\_\_

Medical record No.: \_\_\_\_\_

Sex: Female

Date of birth: --/-- [dd / mm / yyyy]

Pathology: \_\_\_\_\_ molecular type \_\_\_\_\_

T \_\_\_\_\_ N \_\_\_\_\_ M \_\_\_\_\_

ER \_\_\_\_\_ PR \_\_\_\_\_ Her-2 \_\_\_\_\_

Ki-67 \_\_\_\_\_ P53 \_\_\_\_\_

Date of surgery \_\_\_\_\_ surgery type \_\_\_\_\_

Other treatment \_\_\_\_\_

Baseline: date \_\_\_\_\_ statin \_\_\_\_\_

LDL-C \_\_\_\_\_ TC \_\_\_\_\_ TG \_\_\_\_\_ ALT \_\_\_\_\_ CK \_\_\_\_\_ Fatty Liver \_\_\_\_\_

1 month follow-up: date \_\_\_\_\_ statin \_\_\_\_\_

LDL-C \_\_\_\_\_ TC \_\_\_\_\_ TG \_\_\_\_\_ ALT \_\_\_\_\_ CK \_\_\_\_\_ Fatty Liver \_\_\_\_\_

3 month follow-up: date \_\_\_\_\_ statin \_\_\_\_\_

LDL-C \_\_\_\_\_ TC \_\_\_\_\_ TG \_\_\_\_\_ ALT \_\_\_\_\_ CK \_\_\_\_\_ Fatty Liver \_\_\_\_\_

6 month follow-up: date \_\_\_\_\_ statin \_\_\_\_\_

LDL-C \_\_\_\_\_ TC \_\_\_\_\_ TG \_\_\_\_\_ ALT \_\_\_\_\_ CK \_\_\_\_\_ Fatty Liver \_\_\_\_\_

RT (recurrence time)\_\_\_\_\_

Other event\_\_\_\_\_

1 year follow-up: date\_\_\_\_\_statin\_\_\_\_\_

LDL-C\_\_\_\_\_TC\_\_\_\_\_TG\_\_\_\_\_ALT\_\_\_\_\_CK\_\_\_\_\_Fatty Liver\_\_\_\_\_

RT (recurrence time)\_\_\_\_\_

Other event\_\_\_\_\_

1.5 year follow-up: date\_\_\_\_\_statin\_\_\_\_\_

LDL-C\_\_\_\_\_TC\_\_\_\_\_TG\_\_\_\_\_ALT\_\_\_\_\_CK\_\_\_\_\_Fatty Liver\_\_\_\_\_

RT (recurrence time)\_\_\_\_\_

Other event\_\_\_\_\_

2 year follow-up: date\_\_\_\_\_statin\_\_\_\_\_

LDL-C\_\_\_\_\_TC\_\_\_\_\_TG\_\_\_\_\_ALT\_\_\_\_\_CK\_\_\_\_\_Fatty Liver\_\_\_\_\_

RT (recurrence time)\_\_\_\_\_

Other event\_\_\_\_\_

2.5 year follow-up: date\_\_\_\_\_statin\_\_\_\_\_

LDL-C\_\_\_\_\_TC\_\_\_\_\_TG\_\_\_\_\_ALT\_\_\_\_\_CK\_\_\_\_\_Fatty Liver\_\_\_\_\_

3 year follow-up: date\_\_\_\_\_statin\_\_\_\_\_

LDL-C\_\_\_\_\_TC\_\_\_\_\_TG\_\_\_\_\_ALT\_\_\_\_\_CK\_\_\_\_\_Fatty Liver\_\_\_\_\_

RT (recurrence time)\_\_\_\_\_

Other event\_\_\_\_\_

3.5 year follow-up: date\_\_\_\_\_statin\_\_\_\_\_

LDL-C\_\_\_\_\_TC\_\_\_\_\_TG\_\_\_\_\_ALT\_\_\_\_\_CK\_\_\_\_\_Fatty Liver\_\_\_\_\_

4 year follow-up: date\_\_\_\_\_statin\_\_\_\_\_

LDL-C\_\_\_\_\_TC\_\_\_\_\_TG\_\_\_\_\_ALT\_\_\_\_\_CK\_\_\_\_\_Fatty Liver\_\_\_\_\_

RT (recurrence time)\_\_\_\_\_

Other event\_\_\_\_\_

4.5 year follow-up: date\_\_\_\_\_statin\_\_\_\_\_

LDL-C\_\_\_\_\_TC\_\_\_\_\_TG\_\_\_\_\_ALT\_\_\_\_\_CK\_\_\_\_\_Fatty Liver\_\_\_\_\_

5 year follow-up: date\_\_\_\_\_statin\_\_\_\_\_

LDL-C\_\_\_\_\_TC\_\_\_\_\_TG\_\_\_\_\_ALT\_\_\_\_\_CK\_\_\_\_\_Fatty Liver\_\_\_\_\_

RT (recurrence time)\_\_\_\_\_

Other event\_\_\_\_\_
